9.9. Pregnancy

Patients who become pregnant during the study period and up to at least 28 days following chemotherapy or 180 days after the last dose of IMU-131 must not receive additional doses of IMU-131 but may continue other study procedures at the discretion of the investigator.

Patients should be instructed to notify the investigator if it is determined after completion of the study that they or their partner (male patients) became pregnant either during the study or within 28 days following chemotherapy or 180 days after the last dose of IMU-131.

If a pregnancy occurs within 28 days following chemotherapy or 180 days after the last dose of IMU-131, the pregnancy should be followed to term, any premature terminations reported, and the health status of the mother and child including date of delivery and the child's gender and weight should be reported to Imugene Limited after delivery. The mother may freely choose to terminate the pregnancy as her own decision. Neither the Sponsor nor investigators should influence this decision in any way. Similarly, neither the investigators nor Sponsor have the right to intervene or influence

this decision and any ensuing procedures. If this occurs, the termination of pregnancy should be considered an elective surgical procedure and any associated adverse events attributed accordingly.

If the outcome of the pregnancy meets the criteria for an SAE (ie, ectopic pregnancy, spontaneous abortion, intrauterine fetal demise, neonatal death, or congenital anomaly [in a live born, a terminated fetus, an intrauterine fetal demise, or a neonatal death]), the investigator should follow the procedures for reporting SAEs.

Investigational Product: IMU-131
Protocol Identifier: IMU.ACS.001
Protocol Version: Protocol Global Amendment #5, 27 September 2023

9.10. Withdrawal Due to Adverse Events (See Also [Section 6.5: Patient Withdrawal](#))

Withdrawal due to AE should be distinguished from withdrawal due to other causes, according to the definition of AE noted earlier, and recorded on the appropriate AE CRF page.

When a patient withdraws due to an SAE, the SAE must be reported in accordance with the reporting requirements defined in [Section 9.12](#).

9.11. Eliciting Adverse Event Information

The investigator is to report all directly observed AEs and all AEs spontaneously reported by the study patient. In addition, each study patient will be questioned about AEs.

9.12. Reporting Requirements

Each AE is to be assessed to determine if it meets the criteria for SAEs. If an SAE occurs, expedited reporting will follow local and international regulations, as appropriate.

9.12.1. Serious Adverse Event Reporting Requirements

If an SAE occurs, Imugene Limited, or its delegated representative, is to be notified within 24 hours of investigator awareness of the event.

In particular, if the SAE is fatal or life-threatening, notification must be made immediately to Imugene Limited, or its delegated representative, irrespective of the extent of available AE information. This timeframe also applies to additional new information (follow-up) on previously forwarded SAE reports as well as to the initial and follow-up reporting of exposure during pregnancy and exposure via breastfeeding cases.

In the rare event that the investigator does not become aware of the occurrence of an SAE immediately (eg, if an outpatient study patient initially seeks treatment elsewhere), the

investigator is to report the event within 24 hours after learning of it and document the time of his/her first awareness of the AE.

For all SAEs, the investigator is obligated to pursue and provide information to Imugene Limited in accordance with the timeframes for reporting specified above. In addition, an investigator may be requested by Imugene Limited to obtain specific additional follow-up information in an expedited fashion. This information collected for SAEs is more detailed than that captured on the AE CRF. In general, this will include a description of the AE in sufficient detail to allow for a complete medical assessment of the case and independent determination of possible causality. Information on other possible causes of the event, such as concomitant medications and illnesses must be provided. In the case of a patient death, a summary of available autopsy findings must be submitted as soon as possible to Imugene Limited or its designated representative.

Investigational Product: IMU-131
Protocol Identifier: IMU.ACS.001
Protocol Version: Protocol Global Amendment #5, 27 September 2023

9.12.2. Non-Serious Adverse Event Reporting Requirements

All AEs and SAEs that occur after the last informed consent date (i.e. in the case of re-screened patients) will be reported on the AE page(s) of the CRF. It should be noted that an additional form for collection of detailed SAE information will be provided. Where the same data are collected, the forms must be completed in a consistent manner. For example, the same AE term should be used on both forms. AEs should be reported using concise medical terminology on the CRFs as well as on the form for collection of SAE information.

9.12.3. Sponsor Reporting Requirements to Regulatory Authorities

Adverse event reporting, including suspected serious unexpected adverse reactions, will be carried out in accordance with applicable local regulations.

10. DATA ANALYSIS/STATISTICAL METHODS

10.1. Phase 1b Cohort Review Committee (CRC)

Prior to enrollment of patients into the Phase 1b study, a CRC, comprising relevant site investigators, the Medical Monitor, and Sponsor representatives, will oversee safety, cohort evaluation and dose-escalation for the study. A formal charter which will establish the rules, meeting frequency and scope of responsibilities of the CRC will be established for the conduct of the CRC.

After enrollment in Phase 1b begins the CRC will meet in person or by teleconference as soon as feasible after any of the following occur to determine if the criteria for dose limiting toxicity (DLT) has been met:

- One or more patients experience a serious adverse reaction assessed as related to the vaccine by the investigator
- One or more patients experience anaphylaxis
- Two or more patients in a single dose cohort experience an SAE explained by a diagnosis related to vaccination. (For grading of severity see CTCAE v4.03.)

The CRC will review the safety data and make recommendations on the continuation of the study following the procedures outlined in the CRC charter.

All decisions will be documented in the form of minutes.

10.1.1. Phase 1b Definition of Dose-Limiting Toxicity (DLT)

A dose limiting toxicity (DLT) is defined as a drug-related Grade 3 toxicity that cannot be resolved to a Grade 1 with appropriate therapy within 2 weeks, or a Grade 4 or greater toxicity graded by CTCAE v4.03, related to the IMU-131 vaccine.

10.1.2. Phase 1b Dose Escalation

There will be up to 6 patients in each cohort in Phase 1b. The CRC will review data from one complete cycle of chemotherapy (including 3 doses of IMU-131, on Days 0, 14, and 35) for at least 3 patients in a dose cohort to authorize dose escalation.

A staggered enrollment will be used for patient safety, whereby a dose cohort must be completed and reviewed by the CRC before further recruitment. The decision whether to escalate to the next dose cohort will be made by the CRC when at least 3 patients in the current dose cohort have completed chemotherapy cycle 1 (35 days of the study, including 3 doses of IMU-131 on Days 0,14 and 35).

Phase 1b dose escalation will involve 3 dose levels of IMU-131 with a standard 3+3 scheme for determination of safety prior to dose escalation. Patients will receive 3 doses of IMU-131 (Days 0, 14 and 35) with chemotherapy being initiated 14 days after the first dose of IMU-131 with evaluation occurring after the first 21-day cycle of chemotherapy and before opening the enrollment to the next higher dose cohort.

Dose Escalation Decision Rules

- If 0 out of 3 patients with treatment DLT at a given IMU-131 dose level, enter 3 patients at the next dose level;
- If ≥ 2 of 3 patients with treatment related DLT at a given dose level, dose escalation will be stopped. This dose level will be declared the maximally administered dose (highest dose administered). Three (3) additional patients will be entered at the next lower dose level if only 3 patients were treated previously at that dose;
- If 1 out of 3 patients with treatment related DLT at a given dose level, enter at least 3 more patients at this dose level. If 0 of these 3 patients experience treatment related DLT, proceed to the next dose level. If 1 or more of this group suffer treatment related DLT, then dose escalation is stopped, and this dose is declared the maximally administered dose. Three (3) additional patients may be entered at a dose between the current dose and the next lowest dose level, the exact dose of which will be determined by the CRC.

10.2. Phase 1b Analysis

Demographic data of for the study group will be tabulated.

Safety data:

[figure not shown]
Listings will be made of the safety data collected at each time point.

Investigational Product: IMU-131
Protocol Identifier: IMU.ACS.001
Protocol Version: Protocol Global Amendment #5, 27 September 2023

Immunogenicity data:

Immunological data for each time point will be analyzed.

Radiographic data:

Radiographic data for each time point will be analyzed.

10.2.1. Phase 1b Efficacy Analysis

[figure not shown]
The dose effect of IMU-131 will be evaluated in Phase 1b by immunogenicity data: P467-specific antibodies (IgG) and Her-2-specific antibodies (IgG) titers. Additionally, vaccine-specific cytokine responses will be evaluated before and 21 days after the third vaccine dose.

10.2.2. Phase 1b Safety Analysis

The statistical considerations for this study are defined in a detailed Statistical Analysis Plan (SAP). This section focuses on the statistical considerations for the primary objectives. This study and therefore the statistical considerations will be overseen and governed by the CRC and the CRC charter.

The conjecture for Phase 1b is that the cohort receiving the 50 µg dose will have a higher HER2/neu antibody titer than the cohort receiving a lower dose at the assessment time points and that the IMU-131-associated AEs at the 50 µg dose will be acceptable for adoption as recommended phase 2 dose in Phase 2. The study has minimal statistical power for a statistical test ascertaining this conjecture and it will be done descriptively.

10.2.3. Phase 1b Interim Analysis

Investigational Product: IMU-131
Protocol Identifier: IMU.ACS.001
Protocol Version: Protocol Global Amendment #5, 27 September 2023

10.3. Phase 2 Independent Data Monitoring Committee (IDMC)

[figure not shown]
During Phase 2, an IDMC, comprising independent physicians, an independent statistician, the medical monitor, and Sponsor representatives, will monitor data from the study. The medical monitor and Sponsor representatives will only participate in open sessions at IMDC meetings. The IDMC will be scheduled to meet after 8, 16 and 24 progression events occur and at intervals no less than once per year. Further details of the IDMC meetings and review procedures will be contained in the IDMC charter. A formal charter which will establish the rules, meeting frequency and scope of responsibilities of the IDMC will be established for the conduct of the IDMC.

10.4. Phase 2 Analysis

10.4.1. Phase 2 Analysis Populations

- The Intent-to-Treat (ITT) population: All randomized patients. The primary efficacy analysis will be based on this population. ITT analyses will be conducted on the basis of the randomized treatment.
- The Evaluable Set (EVAL): All randomized patients who receive any amount of study treatment and have at least 1 evaluable post-baseline tumor response. EVAL analyses will be conducted on the basis of the randomized treatment.
- The Full Analysis Set (FAS): All randomized patients who receive any amount of study treatment. FAS analyses will be conducted on the basis of the randomized treatment.
- Safety population: All randomized patients who receive any amount of study treatment. All safety analyses will be based on this population. The safety population will be conducted on the basis of the actual treatment received.
- A Per-Protocol (PP) subset may also be used to analyze select efficacy endpoints and will be based on study drug exposure (compliance and/or time on study drug) and major protocol deviations. The criteria for inclusion in the PP subset will be finalized and documented prior to data base lock.

10.4.2. Phase 2 Efficacy Analysis

Investigational Product: IMU-131
Protocol Identifier: IMU.ACS.001
Protocol Version: Protocol Global Amendment #5, 27 September 2023

Analysis of the primary endpoint, OS, and secondary endpoint, PFS, will be performed using the ITT population. Additional secondary and exploratory analyses of efficacy endpoints will be performed using the ITT, FAS, and/or the EVAL sets. Ancillary analyses of select efficacy endpoints may also be performed using the PP set.

The log-rank method will be used to estimate the secondary efficacy parameter of PFS. Analyses of TTP, DCR, ORR, DOR and CTS will be performed using the same methods as described for PFS. The blinded central review disease response assessments will be used as the primary measure for these analyses, and the Investigator disease response assessments will be used as supportive measures for these analyses.

Patients who are continuing in the study at the time of the primary final analysis will continue to be followed per the schedule of assessments until completion of the study; a supplementary analysis may be produced to reflect any additional data collected after the primary final analysis.

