Phase 2 secondary efficacy endpoints:

- PFS measured from randomization to date of earliest progressive disease (PD) based on blinded central review according to RECIST 1.1 criteria, or to date of death from any cause.
- TTP measured from randomization to date of earliest PD based on blinded central review according to RECIST 1.1 criteria.
- DCR measured from randomization as the proportion of patients achieving a confirmed best overall response of complete response (CR), partial response (PR) or stable disease (SD) based on blinded central review according to RECIST 1.1 criteria.
- ORR measured from randomization as the proportion of patients achieving a confirmed best overall response of CR or PR based on blinded central review according to RECIST 1.1 criteria.
- DOR measured from when earliest CR or PR is observed to PD or death due to any cause based on blinded central review according to RECIST 1.1 criteria.

Investigational Product: IMU-131
Protocol Identifier: IMU.ACS.001
Protocol Version: Protocol Global Amendment #5, 27 September 2023

- Percentage CTS measured from randomization as the sum of diameters based on blinded central review according to RECIST 1.1 criteria.

Phase 2 exploratory endpoints:

- Values and changes from randomization in humoral and cellular immunogenicity data including P467-specific antibodies (IgG), Her-2-specific antibodies (IgG), vaccine-specific cytokine levels and regulatory and effector T and B cells.
- Values and changes from randomization in serum prediction markers of tumor progression.
- Values and changes from randomization in Her-2-specific antibodies (IgG) inhibition of in-vitro tumor cell growth.
- Values and changes in intra-tumor T cells and biochemical markers from pre- and post- treatment tumor biopsies.

Phase 2 Safety Endpoints:

- Incidence of treatment-emergent adverse events (TEAEs), Grade 3 / 4 / 5 TEAEs, serious adverse events (SAEs), and TEAEs leading to study treatment discontinuation.
- Incidence of treatment-emergent Grade 3 / 4 clinical laboratory abnormalities.
- Changes and shifts from randomization in clinical laboratory, vital signs, and electrocardiogram (ECG) parameters.
- Change from randomization in ECOG performance grade.
- Concomitant medication use.
- Treatment compliance.

Phase 2 Dose Escalation Primary Endpoint:

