#### **8.2.4. Objective Response Rate (ORR)**

ORR is defined as the proportion of patients with a BOR of CR or PR after randomization.

[figure not shown]

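### Protocol 10.4.2 assigns the PFS log-rank method to DCR, ORR and change in tumor size, which the protocol itself defines as two proportions and a percentage change

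*Protocol*

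**What the plan says.** Protocol 10.4.2 (Phase 2 Efficacy Analysis) has two consecutive sentences. One sets the PFS method: "The log-rank method will be used to estimate the secondary efficacy parameter of PFS". The next extends it: "Analyses of TTP, DCR, ORR, DOR and CTS will be performed using the same methods as described for PFS".

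Protocol 2.2 (Endpoints) fixes the scale of those endpoints. ORR: "ORR measured from randomization as the proportion of patients achieving a confirmed best overall response of CR or PR". DCR has the same form, with stable disease added to the qualifying responses. CTS: "Percentage CTS measured from randomization as the sum of diameters based on blinded central review according to RECIST 1.1 criteria". By contrast, TTP is a time to event: "TTP measured from randomization to date of earliest PD based on blinded central review according to RECIST 1.1 criteria". DOR is also a time to event, starting at the earliest response.

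The SAP does not repeat the protocol sentence. DCR, ORR and CTS have separate sections (8.2.3, 8.2.4, 8.2.7). Section 8.2.4 reads: "ORR is defined as the proportion of patients with a BOR of CR or PR after randomization". The inferential text for the three endpoints is withheld or not shown. SAP section 12 sends the analysis of these endpoints back to the earlier SAP sections.

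**The concern.** A log-rank test compares event-time curves. It needs an event, a time for that event and a censoring rule. A response proportion has no event time in its definition, and a percentage change in sum of diameters has no event at all. Protocol 10.4.2 supplies none of these for DCR, ORR or CTS, so anyone applying the sentence literally would have to invent them, and the result would answer a different question from the one in protocol 2.2.

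Two smaller faults sit beside this. The log-rank is a test, so saying that it estimates PFS is wrong wording. And DOR, although a time to event, exists only in responders, so a between-arm comparison is not one of randomized groups; 10.4.2 carries no such caution.

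At stake is whether the protocol states a usable rule for three of the six secondary efficacy endpoints, and whether protocol and SAP agree.

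**Working it through.** The plan gives no figure to reproduce here; the point concerns the type of method. The check has two parts.

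**1. Scale against method** (definitions from protocol 2.2, method from protocol 10.4.2)

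| Endpoint | Scale | Does the PFS log-rank fit? |
|---|---|---|
| TTP | time to event | yes |
| DOR | time to event, responders only | in form; not a randomized comparison |
| ORR | proportion | no |
| DCR | proportion | no |
| CTS | percentage change, continuous | no |

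The sentence misfits 3 of the 5 endpoints it covers. With PFS itself, that is 3 of the 6 secondary efficacy endpoints.

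**2. What a literal log-rank on ORR would do**

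Inputs: 36 patients allocated 1:1 (protocol 3 and 5.1), so 18 per arm. Scan days 42, 84 and 126 are from protocol 8.4. The response counts, 9/18 on IMU-131 plus chemotherapy and 6/18 on chemotherapy alone, are my assumption, as are the censoring days. ORR is 50.0% against 33.3% in every row below.

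At each event time, with d events among n at risk (n1 on IMU-131, n2 on control): E1 = d·n1/n and V = d(n − d)·n1·n2 / [n²(n − 1)]. Chi-square = (ΣO1 − ΣE1)² / ΣV.

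- **A. All responses on one day, non-responders censored later.** E1 = 15·18/36 = 7.5; V = 15·21·18·18/(36²·35) = 2.25. Chi-square = (9 − 7.5)²/2.25 = 1.00, p = 0.317. This is identical to the Mantel-Haenszel test on the 2×2 table.
- **B. IMU-131 responses at day 42, control at day 126, non-responders censored at day 252.** ΣE1 = 4.5 + 2.0 = 6.5; ΣV = 1.736 + 1.077 = 2.813. Chi-square = 2.5²/2.813 = 2.22, p = 0.136.
- **C. The reverse timing.** ΣE1 = 3.0 + 5.4 = 8.4; ΣV = 1.286 + 1.564 = 2.850. Chi-square = 0.6²/2.850 = 0.126, p = 0.722.
- **D. All responses at day 84, control non-responders censored at day 42, IMU-131 non-responders at day 252.** At day 84, n1 = 18 and n2 = 6. E1 = 15·18/24 = 11.25; V = 15·9·18·6/(24²·23) = 1.10. Chi-square = (9 − 11.25)²/1.10 = 4.60, p = 0.032.

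The p-value runs from 0.032 to 0.722 while ORR does not move. In D the observed count on IMU-131 is below expectation (9 against 11.25), so the test points towards control although IMU-131 has the higher ORR.

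Analysed as a proportion, the same data give one answer: Pearson chi-square 1.03, p = 0.310; Fisher p = 0.500; Wilson 95% intervals 29.0% to 71.0% and 16.3% to 56.3%.

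For CTS there is nothing to compute: without a threshold that turns the percentage into an event, no log-rank is defined, and the protocol gives none.

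**The case against.** The strongest reply is that the SAP, not this sentence, carries the analysis. SAP 8.2.3 derives a best overall response per patient, with categories for no post-randomization assessment and for not evaluable. SAP 8.2.4 defines ORR as a proportion, 8.2.7 is a separate CTS section, and 4.2 gives visit windows for by-visit summaries of change in tumor size. The reference list includes the 1927 paper behind the Wilson interval for a proportion, though the visible text does not show where it is used. This stands, and it limits the point to the protocol sentence.

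A second reply is that protocol 10.4.2 is itself partly withheld: no overall survival method is visible there, so fuller PFS text may exist. That does not rescue the sentence. Whatever else was said about a time-to-event method, it cannot fit two proportions and a percentage change.

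Three stronger readings are tempting, and the documents do not support them.

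- A reader might infer that the secondary analysis cannot be run. Case A shows that a log-rank can be computed on binary data; it is mis-specified, not impossible.
- A reader might infer that the trial has no valid method for these endpoints. The SAP method text is withheld, which does not show that it is missing.
- A reader might infer that, in an open-label trial, the method could be picked after seeing results. SAP section 1 requires finalization and signature before the database lock for the PFS analysis, with significant later changes documented in an amendment.

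It is also fair to say that the documents do not require any particular model for CTS or any particular stratified test for the proportions. Those are choices for the SAP.

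**Conclusion.** The sentence in protocol 10.4.2 is wrong as written. It assigns a time-to-event comparison to DCR, ORR and CTS against the protocol's own definitions, and taken literally its result would depend on response timing and censoring that the endpoints do not contain. The confirmed error is that sentence and the verb attached to the log-rank, not the SAP analysis.

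Severity is low. Only secondary endpoints are affected, and the primary overall survival analysis is untouched. It is still worth correcting. The sentence remains in Amendment 5 (27 September 2023), which is later than SAP 5.0 (12 July 2022), a SAP written to Amendment 3. No visible text in protocol 10.4 says which document prevails if they differ; the protocol's visible pointers to a detailed SAP are in the Phase 1b and dose escalation sections (10.2.2 and 10.6.1).

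The scale mismatch rests on the visible definitions alone. The p-values rest on assumed counts and times and show only that the result can move, not by how much it would in this trial.

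**What to change.** Rewrite the two sentences in protocol 10.4.2:

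- Say that the log-rank method is used to compare PFS between arms, not to estimate it.
- Limit the shared method to TTP and DOR, and note that a between-arm DOR comparison is restricted to responders and is not randomized.
- State that ORR and DCR are analysed as proportions in the ITT set, with patients who have no post-randomization assessment counted as non-responders (ORR) or not controlled (DCR). This also settles the denominator: 10.4.2 now allows ITT, FAS and/or EVAL for these endpoints, and EVAL (10.4.1) drops patients without an evaluable post-baseline response.
- State that CTS is analysed as a continuous percentage change.
- For the details, refer to SAP 8.2.3, 8.2.4 and 8.2.7, after confirming that the withheld text there agrees.

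The cost is a short text change in the protocol. It needs no new data, visits or patients, and it changes no figure in either document.
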